#### 7.2 Labeling, Packaging and Storage

Vials of IP will be provided to the sites in bulk (i.e., individual kits per subject will not be provided). It is forbidden to use IP for purposes other than defined in this protocol.

IP is to be stored refrigerated (2°C to 8°C) in a secure restricted area; avoid freezing. IP will be shipped to sites in controlled temperature shipments with a temperature monitor. Appropriate temperature records will be filed at the site and in the eTMF. It is the responsibility of the PI to verify that IP is within its expiry date before being used.

The external packaging of IP will be labeled with study information (i.e., study number, study Sponsor, name and address of Evolus, Inc., quantity, "CAUTION: Investigational Drug. Limited by Federal law to investigational use", etc.).

The Investigator Brochure will provide all relevant contraindications, hazards, AEs, warnings, and precautions.

#### 7.3 Investigational Product Supply and Accountability

In accordance with 21 CFR Part 312.140 (a) (2), the investigator must maintain accurate records of receipt, use or disposition of a drug that relate to:

- The type and quantity of the drug, the dates of its receipt, and the drug identification (lot number, batch number or code mark);
- The names of all persons who received, used, or disposed of each drug;
- Why and how many units of the drug have been returned to the sponsor or otherwise disposed of.

The sponsor must notify the FDA and IRB of any request that an Investigator return or dispose of any IP. The notice must be made within 30 working days after the request is made and must state why the request was made.

In addition, accurate records will be kept regarding when and how much test article is dispensed and used by each subject in the study. Reasons for departure from the expected dispensing regimen must also be recorded. At the completion of the study, to satisfy regulatory requirements regarding drug accountability, all study drug will be reconciled and retained or destroyed according to applicable regulations.

Unless otherwise confirmed in writing, all used and unused study drug will be returned to Sponsor/designee for destruction at the conclusion of the study. The site monitor will be provided access to the study IP and records for periodic review.

## 8 STUDY TREATMENT

Subjects will be treated either with the study drug 40U of prabotulinumtoxinA or one of the two controls; 20U of prabotulinumtoxinA or 20U of onabotulinumtoxinA.

The study drug and active controls will be prepared, reconstituted, and loaded into the syringes by an appropriate and protocol trained person at the site (i.e., study nurse or other designee). The reconstitution and syringe preparations will be done in a double-blinded fashion.

Using a 25G needle each vial will be constituted, gently, without shaking:

- 20U of onabotulinumtoxinA (control) will be prepared by reconstituting with 1.25 ml of 0.9% sterile, non-preserved saline solution in a 50U vial for a final dilution of 4 U/0.1 ml. After reconstitution, a total of 0.5ml will be drawn up into a 0.5ml syringe.
- 20U of prabotulinumtoxinA (control) will be prepared by reconstituting with 2.5 ml of 0.9% sterile, non-preserved saline solution for a final dilution of 4 U/0.1 ml. After reconstitution, a total of 0.5ml will be drawn up into a 0.5ml syringe.
- The study drug, 40U of prabotulinumtoxinA will be prepared by reconstituting with 0.625 ml of 0.9% sterile, non-preserved saline solution for a final dilution of 8U/0.05 ml. After reconstitution, a total of 0.25ml will be drawn up into a 0.3ml.

Using the preloaded syringe with a 30G needle, the subject is to be injected intra-muscularly into a total of five sites, the mid-line of the procerus, the inferomedial aspect of each corrugator muscle and the superior middle aspect of each corrugator, at least 1 cm above the bony orbital rim (Diagram 1). Both controls (i.e., 20U of prabotlinumtoxinA, 20U of onabotulinumtoxinA) will be injected with 0.1 ml (4U) per site, for a total of 20 U and 0.5 ml. The study drug (i.e., 40U prabotulinumtoxinA) will be injected with 0.05 ml (8U) per site, for a total of 40 U and 0.25 ml.

Topical anesthesia is allowed if required; the type(s) used is to be recorded as a concomitant medication.

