#### 6.2 Subject Randomization

At Visit 2/Treatment Day, subjects will be randomized to a study group utilizing hardcopy computer generated "Randomization Schedules" that will link treatment assignment to each Subject Number. The Randomization Schedule will be maintained by the "Unblinded Injector" (Section 6.3).

The Randomization Schedules will provide for equal randomization (1:1:1 ratio) to treatment with either 20U onabotulinumtoxinA, 20U prabotulinumtoxinA-xvfs, or 40U prabotulinumtoxinA-xvfs.

Subjects will be randomized using a blocked randomization scheme that will be stratified by the following factors:

- Baseline GLS: moderate vs. severe
- Age group:  $\leq 65$  vs. > 65 within each stratum
- Gender: female vs male

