#### 6.3 Blinding

To maintain study blind, the "Unblinded Injector" (i.e., physician or nurse practitioner appropriately skilled in injecting botulinum toxin into the glabellar area and not responsible for subject follow-up) will have access to the Randomization Schedule, be aware of treatment assignment, will prepare syringes of reconstituted IP, and will administer injections of study drug to study subjects.

The Unblinded Injector will be a different individual than the Blinded Evaluator. The Blinded Evaluator and the study coordinators responsible for subject assessment and follow-up, as well as study subjects, will remain blinded to which study treatment was injected.

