3.3. Blinding

To maintain study blind, the "Unblinded Injector" (i.e., physician or nurse practitioner not responsible for subject follow-up) will have access to the Randomization Schedule, be aware of treatment assignment, will prepare syringes of reconstituted IP, and will administer injections of study drug to study subjects.

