4. STUDY TREATMENT

Subjects will be treated either with the study drug 40U of prabotulinumtoxinA or one of the two controls; 20U of prabotulinumtoxinA or 20U of onabotulinumtoxinA.

The reconstitution and syringe preparations will be done in a double-blinded fashion.

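### Syringe preparation is called double-blinded and given to a nurse or designee in one place, and given to the Unblinded Injector in another; blinded preparation is not possible as described

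*Protocol*

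**What the plan says.** On who prepares the syringes, Protocol Section 8 says that study drug and controls are prepared, reconstituted and "loaded into the syringes by an appropriate and protocol trained person at the site (i.e., study nurse or other designee". Protocol Section 6.3 says that the Unblinded Injector will "be aware of treatment assignment, will prepare syringes of reconstituted IP, and will administer injections of study drug to study subjects". The Synopsis repeats this, and SAP Section 3.3 says that the same person "will have access to the Randomization Schedule, be aware of treatment assignment, will prepare syringes of reconstituted IP".

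On whether preparation is blinded, SAP Section 4 states: "The reconstitution and syringe preparations will be done in a double-blinded fashion". Protocol Section 8 carries the same sentence.

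On separation of roles, the Unblinded Injector is described as having no follow-up duties, and Section 6.3 adds: "The Unblinded Injector will be a different individual than the Blinded Evaluator". Section 6.3 also requires the Blinded Evaluator, the coordinators who handle assessment and follow-up, and the subjects to stay blinded. Neither document states the blinding status of the Section 8 preparer, other than by calling the preparation double-blinded.

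**The concern.** The sections disagree on two things: who prepares the syringe, and whether that person knows the arm. A site that follows Section 8 may use a study nurse and may believe, on the protocol's own word, that this nurse is blinded. If the nurse in fact learns the arm, the wall between treatment and assessment depends on the site noticing a problem that the protocol says does not exist.

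This matters because the main outcomes are judgements. The primary endpoint rests on an investigator's rating on the 4-point GLS. The secondary endpoints use subject GLS, GAIS and satisfaction scores. Under Appendix A, coordinators interview subjects and record their responses at remote visits. The primary comparison is prabotulinumtoxinA 40U against 20U, and that is the contrast the filled syringe gives away.

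**Working it through.** **Step 1. Could preparation be blinded as described?** The vial contents are in Protocol Section 7.1 and the diluent and draw volumes in Section 8. Concentration = vial units / diluent volume; dose = concentration × volume drawn; dose per site = dose / 5.

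| Arm | Vial | Diluent | Concentration | Drawn | Dose | Per site |
|---|---|---|---|---|---|---|
| OnabotulinumtoxinA 20U | 50 U | 1.25 ml | 50/1.25 = 40 U/ml (4 U per 0.1 ml) | 0.5 ml | 40 × 0.5 = 20 U | 20/5 = 4 U |
| PrabotulinumtoxinA 20U | 100 U | 2.5 ml | 100/2.5 = 40 U/ml (4 U per 0.1 ml) | 0.5 ml | 40 × 0.5 = 20 U | 20/5 = 4 U |
| PrabotulinumtoxinA 40U | 100 U | 0.625 ml | 100/0.625 = 160 U/ml (8 U per 0.05 ml) | 0.25 ml | 160 × 0.25 = 40 U | 40/5 = 8 U |

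All of the protocol's stated dilutions and doses are reproduced. The differences between arms are therefore internally consistent and do not look like typing errors.

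**Step 2. What does the preparer see?** Section 7.2 says that vials are supplied in bulk, with no individual subject kits. The preparer must choose the product and then add one of three diluent volumes. Each combination belongs to one arm only, so the preparer must know the arm. Section 6.2 has the Unblinded Injector keep the Randomization Schedule, so a separate Section 8 preparer would have to be told the arm; the documents describe no such step.

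**Step 3. What does someone see who only sees the filled syringe?** The two 20U arms look alike by volume and size: 0.5 ml in a 0.5 ml syringe. The 40U arm is 0.25 ml drawn into a 0.3 ml size, and Section 8 confirms: "The study drug (i.e., 40U prabotulinumtoxinA) will be injected with 0.05 ml (8U) per site, for a total of 40 U and 0.25 ml". The filled syringe thus separates 40U from 20U, but not the two 20U arms from each other. Section 10.2.2 has the Blinded Evaluator rate GLS before injection and assess adverse events at the same visit. Neither document says that the syringe is kept out of sight.

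**Step 4. Does any rule settle the conflict?** The SAP's introduction says that the SAP prevails over the protocol. On who prepares, this helps in part, because the SAP names only the Unblinded Injector. On blinding it does not help, because SAP Section 3.3 has a preparer who knows the assignment while SAP Section 4 calls the preparation double-blinded.

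**Step 5. Is an unblinded preparer kept away from assessment?** Indirectly, yes: Section 6.3 requires evaluators and follow-up coordinators to remain blinded, so a person who knows the arm cannot hold those roles without breaching it. Directly, only the Unblinded Injector is separated from follow-up. The indirect rule works only if the site recognises its preparer as unblinded, and the double-blinded label says the opposite.

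**The case against.** The other side has a good deal to say. The Section 8 phrase covering other designees can be read to include the Unblinded Injector, which would remove much of the conflict over who prepares. The SAP never mentions a study nurse. Section 6.3 already requires assessors and follow-up coordinators to be blinded. No section gives a preparer a rating task; the primary GLS rating belongs to the Blinded Evaluator.

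These points stand, and they rule out several stronger readings that a reader might infer:

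- That nothing stops a preparer from assessing subjects. Section 6.3 does stop it, through the blinding required of the assessing roles. What is missing is an explicit statement about the preparer.
- That all 150 subjects' ratings are compromised if Section 8 is followed. Following Section 8 unblinds the preparer. Ratings are exposed by that route only if the preparer also assesses or coordinates, contrary to Section 6.3, or passes on the allocation.
- That any bias would favour 40U. The documents give no basis for a direction or a size.
- That subjects are unblinded by seeing the syringe. Each subject is treated once and would have to know the volumes used in each arm. This exposure would also exist if Section 6.3 were followed exactly, so it is no evidence for the conflict over who prepares.

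What the objection does not answer is the blinding claim itself. However the other designee is read, one person cannot prepare under blind and also know the assignment.

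**Conclusion.** The point holds as an internal contradiction and as a claim of blinding that the design cannot deliver. Double-blinded preparation is incompatible with bulk vials, two products and arm-specific diluent volumes, and the 40U arm is also marked by its draw volume and syringe size. The SAP-prevails rule does not resolve this, since both statements about blinding are in the SAP.

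The consequence is a risk, not a demonstrated bias. The false label weakens the indirect protection in Section 6.3 for subjective outcomes, on the 40U versus 20U contrast that the trial treats as primary. No effect on ratings can be calculated from the documents, and no sample-size, power or alpha figure depends on the point. It should be corrected because sites work from the protocol and the correction costs only wording. The conclusion assumes that vials are handled as Section 7.2 describes, with no coding or masking step set out elsewhere.

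**What to change.** Reconcile the Synopsis, Protocol Sections 6.3 and 8, and SAP Sections 3.3 and 4 so that they agree on who prepares the syringes. Then:

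1. Delete the double-blinded description of preparation from Protocol Section 8 and SAP Section 4.
2. State that anyone who prepares or handles the syringe is unblinded and takes no part in GLS, GAIS, SSS or adverse event assessment, or in follow-up coordination.
3. Require the filled syringe to be kept out of sight of the subject and the Blinded Evaluator, because its volume and size separate 40U from 20U.

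If subjects have already been treated, sites' records of delegated duties can be checked to see whether anyone who prepared syringes also assessed or coordinated follow-up.

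The cost is protocol and SAP wording, plus one staffing constraint: the preparer cannot also serve as evaluator or follow-up coordinator. An unblinded role is already planned, so the constraint should be modest. Product, dose and volume are unchanged.

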**Diagram 1: Injection Sites** 

#### 8.1 Concomitant Medications

All treatment/procedures received by the subject within 14 days prior to Visit 2 (Treatment Day) and throughout the treatment period, including the name of the treatment/procedure, must be recorded in the eCRF with start date, stop date, dosage, frequency and indication, if applicable.

Medications that may interfere with neuromuscular transmission (e.g., aminoglycosides, curarelike agents) or muscle relaxants need to be observed closely since botulinum toxin may potentiate the effects. Botulinum toxin may also potentiate the systemic anticholinergic effects of anticholinergic drugs. If any of these medications are taken, the Investigator will ensure that all appropriate therapy and follow-up for the subject is provided.

If prohibited therapies and/or procedures are administered during the study, the Medical Monitor will be contacted to discuss details of the event. At a minimum, the event will be documented by the site staff as a protocol deviation, as instructed by the Medical Monitor. Depending upon the nature of the prohibited therapy and the timing relative to the determination of the primary endpoint, the Medical Monitor may decide to discontinue the subject.

The decision to administer a prohibited medication/treatment is done with the study subjects' safety as the primary consideration. If permissibility of a medication/treatment is in question, the Medical Monitor should be contacted before the prohibited medication/treatment is administered.

#### 8.1.1 **Prohibited and Restricted Medications**

As per Exclusion Criteria (Section 5.2), subjects are prohibited from using various medications or undergo various procedures while enrolled in the study from Visit 1 until study exit.

The following medications/procedures have either restriction for usage and/or are prohibited during the course of the study, and appropriate washout periods noted below must be respected:

Treatment/Procedure	Washout	During Study
Botulinum toxin injections (any serotype) above the level of the lateral canthus	$\geq 6$ months	Prohibited
Botulinum toxin injections (any serotype) in any other body region below the level of the lateral canthus	n/a	Prohibited
Any facial aesthetic procedure (e.g., injection with biodegradable fillers, chemical peeling, photo rejuvenation, etc.) in the glabellar area	$\geq 12$ months	Prohibited
Insertion of permanent material in the glabellar area	Any previous use prohibited	Prohibited
Energy based or cryotherapy-based treatment of facial muscles superior to the lateral canthus	Any previous use prohibited	Prohibited
Surgery in the glabellar area including surgical removal of the corrugator, procerus, or depressor supercilii muscles, or a combination of these, or scars in the glabellar area and the surrounding areas (including eyebrow)	Any previous surgery prohibited	Prohibited
Any planned facial aesthetic procedure superior to the level of the lateral canthus (can continue with their usual skin care routine)	n/a	Prohibited
Exposure to any other investigational drug/device	$\geq 30 \ days$	Prohibited

## 9 DATA COLLECTION

#### 9.1 Electronic Case Report Form

Treatment and follow-up of subjects will be recorded in a 21 CFR part 11 compliant eCRF. Data will be first recorded into the medical record and study specific source document worksheets prior to entry into the eCRF. The study coordinator will refer to these worksheets in conjunction with the medical record in order to complete data entry into the eCRF.

In order to review and electronically sign the eCRF, the PI will have an individual login password that will allow him/her to view data that has been generated. The PI must ensure that he/she electronically signs for completed eCRFs on a timely basis.

#### 9.2 Coding

Adverse Events will be coded using the current MedDRA dictionary. Concomitant medications will be coded using the current WHODrug dictionary.

### **10 STUDY EVALUATIONS**

#### **10.1 Informed Consent**

The PI (or designate) will explain the benefits and risks of study participation to each subject. Written informed consent must be obtained prior to any study related procedure.

#### **10.2** Visit Procedures

#### 10.2.1 Visit 1 (Screening Visit; ≤14 Days)

Subjects can be treated any day after initial screening (within 14 days), including the day of screening at the discretion of the Investigator. The following screening assessments will be conducted at Visit 1:

- Written informed consent
- Inclusion / exclusion criteria
- Demographics and medical history (including previous use of botulinum toxins)
- Brow Area Photography (Section 10.3.4)
- Effectiveness Evaluations Investigator (Blinded Evaluator)
   GLS (max frown) (Section 10.3.1)
  - Effectiveness Evaluations Subject
  - GLS (max frown)
- Safety Assessments
  - Directed Questionnaire (Section 10.4.1)
  - Directed Review of Systems (Section 10.4.2)
  - Vital Signs (Section 10.4.3)
  - Physical Exam (Section 10.4.4)
  - UPT (if female subject of childbearing potential) (Section 10.4.5)
  - Clinical Laboratory Tests (Section 10.4.6)
  - ECG (Section 10.4.7)
  - Concomitant Medications (Section 10.4.9)

#### 10.2.2 Visit 2 (Treatment Day)

Subjects who successfully complete screening and sign the informed consent will be treated with 20U onabotulinumtoxinA, 20U prabotulinumtoxinA, or a 40U prabotulinumtoxinA. At the discretion of the Investigator, the screening visit and first treatment visit may take place on the same day. The following assessments and procedures will be conducted at Visit 2:

- UPT (if female subject of childbearing potential)
- Brow Area Photography
- Effectiveness Evaluations Investigator (Blinded Evaluator)
   GLS (max frown) prior to injection
- Effectiveness Evaluations Subject
  - GLS (max frown) prior to injection
- Randomization to study treatment and IP injections (Unblinded Injector)
- Effectiveness Evaluations Subject
  - 7-Day Subject Diary (Section 10.3.5)
- Safety Assessments Investigator (Blinded Evaluator)
  - Concomitant Medications
  - Adverse Events (Section 10.5)

#### 10.2.3 Visit 3 (Safety and Effectiveness Follow-up; 48hrs ±0 day)

- Brow Area Photography
- Effectiveness Evaluations Investigator (Blinded Evaluator)
  - GLS (max frown)
  - GAIS (Section 10.3.2)
- Effectiveness Evaluations Subject
  - GLS (max frown)
  - GAIS
  - Subject Satisfaction (Section 10.3.3)
  - 7-Day Subject Diary
- Safety Assessments Investigator (Blinded Evaluator)
  - Directed Questionnaire
  - Directed Review of Systems
  - Vital Signs
  - Physical Exam
  - Concomitant Medications
  - Adverse Events

### 10.2.4 Visit 4 (Phone Follow-up; Day 7 ±1 day)

- Safety Assessments
  - Safety Assessment Phone Call (Section 10.4.8)
  - Concomitant Medications
  - Adverse Events

### 10.2.5 Visits 5 to 15 (Visits each 30 Days; V5 $\pm$ 3 days, V6 to V15 $\pm$ 7 days)

Subjects will continue to be monitored for safety and effectiveness at one-month intervals. On and after **Day 90**, subjects are eligible to exit the study once their GLS score at maximum frown has returned to Baseline (Investigator assessment). Subjects will return for monthly assessments until they reach their Baseline GLS score (Investigator assessment). Assessment procedures include:

- Brow Area Photography
- Effectiveness Evaluations Investigator (Blinded Evaluator)
  - GLS (max frown)
  - GAIS
- Effectiveness Evaluations Subject
  - GLS (max frown)
  - GAIS
  - Subject Satisfaction
  - Clinical Interview (Visit 5; Day 30 only) (Section 10.3.4)
- Safety Assessments Investigator (Blinded Evaluator)
  - Directed Questionnaire
  - Directed Review of Systems
  - Vital Signs
  - Physical Exam
  - Concomitant Medications
  - Adverse Events

### 10.2.6 Visit 16 (Final Visit or ET Visit; Day 365 ±14 days)

The Final visit (or ET visit) will take place when subjects GLS score (Investigator assessment) has returned to Baseline. Subjects may withdraw from participation in the study at any time for any

reason. If withdrawal occurs, the subject should be asked to complete a follow-up or early termination visit, if possible. During the final or early termination visit, both safety and effectiveness evaluations will be performed as follows:

- Brow Area Photography
- UPT (if female subject of childbearing potential)
- Effectiveness Evaluations Investigator (Blinded Evaluator)
  - GLS (max frown)
  - GAIS
- Effectiveness Evaluations Subject
  - GLS (max frown)
  - GAIS
  - Subject Satisfaction
  - Clinical Interview
- Safety Assessments Investigator (Blinded Evaluator)
  - Directed Questionnaire
  - Directed Review of Systems
  - Vital Signs
  - Physical Exam
  - Clinical Laboratory Tests
  - ECG
  - Concomitant Medications
  - Adverse Events

#### 10.2.7 Unscheduled Visit

An unscheduled in-office visit may occur at any time during the study to complete missed study procedures, assess adverse events, or assess ongoing unresolved drug-related adverse events after study exit. During the visit, some or all of the safety and effectiveness evaluations may be performed as follows:

- Brow Area Photography
- Effectiveness Evaluations Investigator (Blinded Evaluator)
  - GLS (max frown)
  - GAIS
- Effectiveness Evaluations Subject
  - GLS (max frown)
  - GAIS
  - Subject Satisfaction
  - Clinical Interview
- Safety Assessments Investigator (Blinded Evaluator)
  - Directed Questionnaire
  - Directed Review of Systems
  - Vital Signs
  - Physical Exam
  - Clinical Laboratory Tests
  - *ECG*
  - Concomitant Medications
  - Adverse Events
